### *Randomization:*

Participants will be assigned a randomization number once the following has been accomplished: eligibility has been verified at the site level, eligibility has been confirmed by the site PI, and eligibility CRF has been entered into the DMI web application. The randomization number will be generated by the database and assigned to the participant. Refer to Section 13.2 for details of randomization.

### *Baseline/Registration/Randomization into site-specific databases:*

The DMI is the database of record for the study. Registration and randomization should occur per the procedures outlined above. If the site staff need to enter study data into site-specific electronic databases per their institutional requirements, they should do so in accordance with their institutional policies and procedures.

Appropriate CRFs must be completed for any participant who signs an informed consent. If a consented participant is a screen failure and deemed ineligible, the following CRFs must be completed: 1) the Registration CRF with the eligibility box checked “no”, 2) the Inclusion and Exclusion CRFs showing why the participant is ineligible, 3) the Off-Study CRF, 4) the Adverse Event CRF, 5) the Concomitant Medication CRF and 6) the Verification CRF. If no Adverse Event and/or Concomitant Medications were assessed by the time the participant is deemed ineligible, the “NONE” box will be checked to complete both CRFs. All participants who sign an informed consent must formally go off study. All participant registration information will be entered into DMI. If a participant experiences a serious adverse event during the screening process, an SAE form must be completed.

## 6.9 Blinding and Unblinding Methods

- Participants will be blinded to aspirin or placebo.
- The Statistician and the Study Pharmacist will not be blinded to Aspirin or placebo.
- All other Investigators will be blinded to Aspirin or placebo.
- The MDACC Data and Safety Monitoring Board will also be blinded unless unblinding is warranted (the reasons for unblinding are outlined below).
- All participants will take 1 tablet per day of aspirin/matching placebo.
- Study assignments will be unblinded to the Study Investigators and Site Coordinators after all of the data are collected and the study database has been locked. Unblinding will also occur if the participant’s physician deems that unblinding is necessary, such as in the case of unacceptable toxicity thought to be related to the study agent or progressive disease, or if the participant becomes pregnant.
- Unblinding will only take place after consultation with the NCI, DCP Task Order Monitor [name].
- If unblinding is indicated prior to the completion of the study, it will be conducted as follows:
  - The Site PI contacts the Protocol Chairman (the Protocol Principal Investigator) and requests the participant’s treatment status be unblinded.
  - The Protocol Chairman (the Protocol Principal Investigator) contacts the NCI, DCP Task Order Monitor (Medical Monitor) and requests the participant’s treatment status be unblinded. The Protocol Chairman then conveys the Task Order Monitor’s decision to the Site PI. The Site PI then proceeds with unblinding as written out below.
  - If the NCI Task Order Monitor cannot be reached and the participant requires emergency care, the Protocol Chairman (the Protocol Principal Investigator) may authorize the site PI to break the blind.
  - If the Site PI is unable to reach the Protocol Chairman and the participant requires emergency care, then the Site PI must proceed with unblinding as written out below.
  - The Site PI requests the participant’s treatment status be unblinded by the research pharmacist (or designated individual responsible for dispensing drug).
  - The Site PI officially takes the participant off-study.
  - The date and reason for breaking the blind must be submitted by the Site PI to the Protocol Chairman, [name], as soon as possible.
  - It is the responsibility of the Study Chairman to report the date and reason for breaking the blind to the **NCI Task Order Monitor**, [name], as soon as possible.
  - The date and reason for breaking the blind must be submitted by the Study Chairman to the MD Anderson Consortium Principal Investigator, [name], PhD, or

designee as soon as possible via email to [[contact]](mailto:[contact]) and [[contact]](mailto:[contact]) or phone at [contact].

- The date and the reason for breaking the blind will be reported by the MD Anderson Consortium Principal Investigator or designee to the MD Anderson DSMB as soon as possible.

## 6.10 Agent Destruction/Disposal

### *EIO*

At the completion of investigation at EIO, all unused study agent together with all returned tablets will be returned to the Pharmacy Service and kept till destruction. Documentation of disposal and destruction will be kept until the end of the trial.

### *MDACC*

At the completion of investigation at MD Anderson, all unused study agent will be returned to NCI, DCP Repository according to the DCP “Guidelines for AGENT RETURNS” and using the DCP form “Return Drug List”. The guidelines and the form are available on the DCP website.

## 7. CLINICAL EVALUATIONS AND PROCEDURES

### 7.1 Schedule of Events

On a weekly basis, all subjects participating in the ongoing IEO screening programs COSMOS 1 and COSMOS2 presenting lung nodules are discussed during multidisciplinary meetings involving radiologist and clinicians in order to assess the most appropriate monitoring schedule.

In addition, subjects with eligible subsolid lesions identified outside the context of a screening program will be discussed to select potential participants.

Subjects presenting one or more persistent subsolid lung nodules according to the inclusion criteria (see par 4.1) are eligible for this chemoprevention trial. At EIO, potential candidates will be contacted by phone by trained personnel illustrating the possibility of taking part in a chemoprevention trial and scheduling an appointment for an outpatient visit at the Institute. Randomization should be performed within 2 months (i.e., 61 days) from the CT scan. An exception may be done for those subjects with nodules who are eligible at the CT scan performed 3 months apart: in order to maintain 12 months treatment period, these subjects will be randomized within 6 weeks (i.e. 42 days) and will repeat the CT scan 12 months after.

At MDACC, subjects with persistent subsolid lung nodules detected during any of the screening programs are potentially eligible for the trial and will be identified as potential candidates for the study by the Lung Cancer Screening program coordinator. In addition, subjects with subsolid lesions identified outside the context of a screening program will be provided to the research staff by the collaborating radiologists creating a future recruitment resource upon subsequent CT for stability. While waiting for subsequent CT scan, the potential candidate will be given a leaflet about the possibility of being contacted for taking part in a prevention trial. Both standard dose and low dose CT scans are allowed provided that the same procedure is used at both time points.

#### Baseline and Randomization:

- Signed informed consent.

- Collection of a blood samples (safety including  $\beta$ -HCG if applicable, biomarkers including TXB2 and biorepository), urine samples (biomarkers), physical exam and medical history including baseline symptoms; concomitant medications; confirmation of eligibility criteria
- Participants are randomized to receive either study agent or placebo and will be given a 7-month supply of drug or placebo (a kit containing 7 bottles of drug or placebo, with 30 tablets in each bottle, 1 tablet per day) together with a daily calendar.

Month 1 (+/- 1 weeks from randomization):

Phone contact in order to:

- record concomitant medications and record and evaluate adverse events;
- record self-reported compliance.

Month 3 (+/- 2 weeks from randomization):

Phone contact in order to:

- record concomitant medications and record and evaluate adverse events;
- record self-reported compliance.
- confirm date of the next schedule clinic visit and blood/urine tests
- CT scan if determined to be needed during multidisciplinary meetings

Participant will be asked to return used and unused boxes at the month 6 visit.

Month 6 (+/- 2 weeks from randomization):

- Participants will undergo physical exam, vital signs, weight, lab test (including  $\beta$ -HCG, if applicable) and biological sample collection (blood, urine) for biomarker measurement including TXB2.
- Concomitant medications will be recorded and adverse events will be recorded and evaluated.
- Compliance will be measured (subjects will be asked to return both used and unused bottles as well as calendar).
- CT scan if determined to be needed during multidisciplinary meetings

A 7-month supply of drug or placebo will be provided (a kit containing 7 bottles of drug or placebo, with 30 tablets in each bottle, 1 tablet per day).

Month 9 (+/- 2 weeks from randomization):

Phone contact in order to:

- confirm date of the next CT scan and month 12 clinic visit and ;
- record concomitant medications and record and evaluate adverse events;
- record self-reported compliance.

Month 12 (+/- 2 weeks from randomization):

- Participants will undergo physical exam, vital signs, weight, lab test and biological sample collection (blood and urine) for biomarker measurement including TXB2 and biorepository.
- Concomitant medications will be recorded and toxicity will be evaluated.
- Compliance will be measured (subjects will be asked to return both used and unused bottles as well as the calendar).
- CT scan will be performed.

Month 13: Phone contact; adverse events and concomitant medication will be recorded and evaluated.

## SCHEUDLE OF EVENTS

Evaluation/ Procedure	Pre-study evaluation	Baseline Visit/Registration	Randomization	Month 1	Month 3	Month 6 visit	Month 9	Month 12 visit	Month 13	Early Termination
Informed Consent		X								
Assess pre study Eligibility (CT scan)	X									
Assess Eligibility		X								
Medical History		X								
Physical Exam/ height/weight/ vital signs		X				X		X		X
Interim medical history						X		X		X
Tobacco use assessment		X				X		X		X
Laboratory Tests		X				X		X		X
Biomarkers*§ (blood, urine)		X				X		X		
Biorepository (blood)		X						X		
CT scan					(X)¶	(X)¶		X		
Concomitant Medications	X		X	X	X	X	X	X	X	X
Baseline symptoms	X									
Dispense Study Agent			X			X				
Collect study agent						X		X		X
Compliance				X°	X°	X	X°	X		X
Review Agent Diary/Record			X			X		X		X
Adverse Events				X	X	X	X	X	X	X
Phone contact				X	X		X		X	

§Biomarkers collection at baseline, 6 and 12 month visit requires the subject to have fasted for at least 6 hours and includes TXB2 measurement; \*Blood for miRNA and urine for LTE4 and PGEM will be collected and measured at baseline and month 12 only; ° review of self reported compliance; Serum pregnancy test will be done only on potentially fertile women by β-HCG measurement; ¶ if determined to be needed during COSMOS multidisciplinary meetings

## 7.2 Prestudy Evaluation/Baseline Visit/Registration

Pre study evaluation is:

- Measurement of subsolid nodules detected at any qualifying CT scan (for details see section 7.6)

Baseline exams are:

- Fasting blood lab tests (hemogram, AST, ALT, Na, K, glucose, BUN, total bilirubin, Cl, Ca, alkaline phosphatase, creatinine, β-HCG, if applicable)
- Physical exam and medical history; for the purpose of the present study, minimal requirements for the physical exam visit include the following body/system sites: appearance, chest, lungs, heart and abdomen.
- Fasting (at least 6 hours) blood sample collection for biomarkers, biorepository and baseline level of serum TXB2
- Urine sample collection for urinary creatinine and for biomarkers
- At baseline clinic visit, participants will be instructed on the importance of drug compliance. Participants will be provided and instructed on the use of a pill diary to be completed daily, signed and dated by the participant. Participants will be informed that a pill count will be conducted on their study medication use so that their study medication bottle with remaining tablets must accompany them in the subsequent clinic visit.

### 7.3 Evaluation During Study Intervention

During study intervention, participants will undergo physical exam, interim history, vital signs, weight, tobacco use assessment, in a dedicated outpatient clinic at month 6. Phone contact will occur on month 1, 3, and 9.

Safety blood lab tests (hemogram, AST, ALT, Na, K, glucose, BUN, total bilirubin, Cl, Ca, alkaline phosphatase, creatinine,  $\beta$ -HCG, if applicable) will be performed at month 6.

Fasting (at least 6 hours) biological samples (blood and urine) will be collected at month 6 for biomarker measurement including TXB2. Samples will be stored until measurement.

### 7.4 Evaluation at Completion of Study Intervention

Participants will undergo CT scan, physical exam, interim history, vital signs, weight, tobacco use assessment, in a dedicated outpatient clinic at month 12.

Safety lab tests (hemogram, AST, ALT, Na, K, glucose, BUN, Total Bilirubin, Cl, Ca, Alkaline phosphatase, creatinine,  $\beta$ -HCG, if applicable) will be performed at month 12.

Fasting (at least 6 hours) blood samples will be collected at month 12 for biomarkers measurement including TXB2 and biorepository. Samples will be stored till measurement.

Urine sample will be collected for urinary creatinine and for biomarkers. Samples will be stored till measurement.

### 7.5 Post-intervention Follow-up Period

Participants will be contacted with a phone call at month 13, i.e. 1 month after the final CT scan, to check about adverse events and concomitant medication.

After that, subjects will continue the CT scan evaluation as needed

### 7.6 Methods for Clinical Procedures

#### Assessment of lung nodules with low dose CT scan at IEO

Investigations will be performed with low-dose CT scans (average effective dose  $<1.5$  mSv, without contrast medium), with a multidetector (64 slices) CT scanner (CT750 HD/Optima 660, General Electric Healthcare, USA) with the following parameters:

- 120 Kvp, 30 mA
- Matrix 512x 512
- pitch 1.75
- 2.5 mm thickness
- Soft tissue algorithm
- single breath, in respiratory apnoea
- retro-reconstruction at 1.25 mm interval
- at the end of a session of 15 - 20 subjects the investigations will be sent to the workstation and archived both on hard-disk and on CD in DICOM format.

- multiplannar reconstruction and 3-dimensional volume reconstruction will be performed on the workstation (Advantage Windows 4.2, General Electric medical system)

Nodule volumes and volume doubling time (VDT) will be automatically calculated by Lung VCAR specific software (GE healthcare). In absence of available volumetry by the software, VDT will be calculated by the following formula using the maximum diameter.

$$VDT = \frac{\log_{10} 2 \times (\text{difference in days between first CT and second CT})}{3 \times \log_{10} (\text{difference in nodule size [mm] between first CT and second CT})}$$

Lung nodule maximum and mean density will be measured by the software lung VCAR (GE) before and after treatment.

Within 6 days an expert radiologist will read the images on the workstation through the windows for lung parenchyma (WW 1500, WL -650) and with MPVR (maximum projection visual resolution) reconstruction and mediastinum windows (WW 400, WL 40). A comparison between first year and baseline CT scan will be performed by Cosmos radiologists. All exams which show persistence of previous identified subsolid lung nodules will be discussed in a specific meeting with a senior radiologist (chemoprevention trial-responsible) and a senior thoracic surgeon (chemoprevention trial-responsible) within 10 days of the CT investigation. Eligible cases for the chemoprevention trial according to the criteria in section 4.1 and 4.2 are scheduled for the preliminary phone contact.

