## 4. PARTICIPANT SELECTION

### 4.1 Inclusion Criteria

4.1.1 Asymptomatic current or former smokers (having stopped within the last 20 years). See Appendix D

4.1.2 Age  $\geq$  50 years (risk of lung cancer in subjects under 50 is low thus screening is not indicated by actual international guidelines).

4.1.3 Smoking history  $\geq$  20 pack/years; subjects must be included in an ongoing annual screening with low dose CT scan **or**

must have two consecutive CT outside the context of a screening program confirming subsolid nodules as per inclusion criteria number 4.1.4.

4.1.4 Subjects must have subsolid (non solid or partially solid) nodules with size between 4 and 10 mm with any Volume Doubling Time (VDT) not candidate to surgical excision **and/or**

subsolid (non solid or partially solid) nodule larger than 10 mm with VDT higher than 400 days and not candidate to surgical excision.

4.1.5 All nodules should be persistent at least after three months follow up with CT; a reduction up to 15% of the diameter of the largest target nodule from the previous CT scan is allowed

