## 13.2 Randomization/Stratification

In order to keep at minimum the imbalance in treatments a stratified blocked randomization strategy will be used considering only the relevant prognostic factors. Subjects will be stratified according to screening vs non screening CT scan, gender, smoking habits (current versus former smokers) and nodule type (non solid versus partially solid nodules). A blocked randomization will be done within each stratum. Other possible prognostic factors are age, the number of lesions, their volume doubling time and their size but since there is no evidence that they affect the response probability they will be included just in a stratified analysis, not during the randomization process.

Justification of stratification:

Stratification by nodule type and smoking status is planned because both non solid type and active smoking are associated with the risk of developing lung malignancies and their natural history, while stratification by screening vs non screening CT scan, and gender are conservative. The effect of aspirin has been variable in men and women for the prevention of certain conditions.

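### The fallback volume doubling time (VDT) formula takes the log of a diameter difference in mm instead of a diameter ratio, so growing nodules over 10 mm that meet the 400-day condition nearly always read too low or unusable

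*Combined protocol and SAP*

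**What the plan says.** Protocol section 7.6, under the heading for low-dose CT at the EIO, has the Lung VCAR software calculate nodule volume and VDT automatically. It then gives a fallback: "In absence of available volumetry by the software, VDT will be calculated by the following formula using the maximum diameter". The fallback divides log10(2) times the days between scans by 3 times log10 of the "difference in nodule size [mm] between first CT and second CT". No other section restates or corrects it, and no worked value is given.

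VDT enters the plan in these places:

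- Section 4.1.4 admits a subsolid "nodule larger than 10 mm with VDT higher than 400 days and not candidate to surgical excision". The alternative class, joined by and/or, is "nodules with size between 4 and 10 mm with any Volume Doubling Time (VDT) not candidate to surgical excision".
- Section 4.1.5 requires persistence for at least three months and adds that "a reduction up to 15% of the diameter of the largest target nodule from the previous CT scan is allowed".
- Section 13.2 reserves some variables for a stratified analysis: "Other possible prognostic factors are age, the number of lesions, their volume doubling time and their size".
- Appendix C uses VDT cut-offs of 400 and 600 days for scan intervals, without saying how that VDT is obtained.

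**The concern.** A doubling time comes from the log of a volume ratio. If volume scales with the cube of diameter, that log is 3 times the log of the diameter ratio, which is where the 3 comes from. A difference in mm cannot take the ratio's place. Its log depends on the unit chosen, and the result no longer depends on how large the nodule was to begin with. The stated unit, and the parallel wording for the difference in days, make a text-extraction fault unlikely.

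This is the only written method when volumetry is missing, and it feeds an inclusion condition. Followed literally, it would turn away growing nodules over 10 mm that meet the 400-day condition, or return a number that cannot be read against 400. A stratified analysis by VDT could also misplace nodules of any size.

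**Working it through.** **Inputs.** The formula and its use of maximum diameter are from section 7.6. The 400-day threshold and the 10 mm boundary are from 4.1.4. The shortest scan interval is three months (4.1.5, taken as 90 days) and the usual screening interval is one year (section 2.3, taken as 365 days). Diameters, the 180-day interval and the recording step are my assumptions. The plan gives no VDT figure to reproduce.

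**Formulas**, with t in days, d1 and d2 the diameters in mm, and g = d2 - d1:

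- Ratio form: VDT = t × 0.30103 / (3 × log10(d2/d1))
- Printed form: VDT = t × 0.30103 / (3 × log10(g))

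**Worked cases**

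| d1 to d2 (mm) | Days | Ratio form | Printed form |
|---|---|---|---|
| 11 to 13 | 365 | 505 | 122 |
| 20 to 22 | 365 | 885 | 122 |
| 11 to 11.5 | 90 | 468 | -30 |
| 12 to 13 | 365 | 1054 | division by zero |
| 11 to 12.05 | 90 | 228 | 426 |
| 8 to 8.5 | 365 | 1391 | -122 |

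First row in full: 365 × 0.30103 = 109.88. Dividing by 3 × log10(13/11) = 0.2177 gives 505; dividing by 3 × log10(2) = 0.9031 gives 122. Rows one and two show that baseline size drops out of the printed form. Row five shows the error running the other way.

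**Growth that gives VDT above 400.** Setting VDT > 400:

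- Ratio form: g < d1 × (2^(t/1200) - 1)
- Printed form: 1 < g < 2^(t/1200), whatever d1 is

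| Days | Printed form passes (mm) | Ratio form passes, d1 = 11 mm |
|---|---|---|
| 90 | 1 to 1.05 | up to 0.59 |
| 180 | 1 to 1.11 | up to 1.21 |
| 365 | 1 to 1.23 | up to 2.58 |

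At 90 days the two ranges do not overlap for an 11 mm nodule.

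**Share of qualifying growth values read correctly (d1 = 11 mm, 365 days).** In 0.1 mm steps there are 25 qualifying values, 0.1 to 2.5 mm. The printed form puts 2 above 400 (1.1 and 1.2 mm), puts 13 between 0 and 400, makes 9 negative and is undefined for 1. In 0.5 mm steps it reads 0 of 5 correctly, and in 1 mm steps 0 of 2. With growth spread evenly over the qualifying range, baseline 10 to 20 mm and intervals of 90 to 730 days, the printed form passes 0% to 10% of that range. If the 10 mm boundary refers to the second scan instead, it passes 0% to 12% (second-scan diameter 10.1 to 15 mm, 90 or 365 days). These are shares of a millimetre range, not of candidates.

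**Nodules that do not grow.** A change from 11 to 9.35 mm (-15%) in 90 days gives -128 days by the ratio form and no value by the printed form. An unchanged diameter is undefined under both. The plan needs a stated reading for these cases whichever form is used.

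**The case against.** The formula applies only where the software gives no volumetry, at a frequency the plan does not state, and it is printed only under the EIO low-dose heading. For entry it touches only nodules over 10 mm, and a subject may still qualify through a smaller nodule. A senior radiologist and a thoracic surgeon discuss persistent subsolid cases, and negative or infinite values are conspicuous, so staff may already use the ratio. Eligibility is settled before randomisation, so the comparison of aspirin with placebo is not biased. Section 13.2 names VDT only as a possible factor, without cut-offs, and section 13.8 foresees no subgroup analyses. All of this stands and limits the consequence. It does not make the printed formula usable, and an unwritten correction cannot be checked against the protocol.

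A sharper objection is that counting negative results as failures assumes a convention the plan lacks. That is fair for the 9 negative values among the 25. The 13 positive values at or below 400 are wrong under any convention. Reading negative as meeting the condition would create the opposite error: 11 to 11.9 mm in 90 days has a ratio VDT of 264 but prints as -197, and would then pass. For the same reason, the expectation that nodules which should fail mostly still fail holds only if a negative value is not taken as above 400.

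**Conclusion.** The error is real and should be fixed. The fallback formula is invalid as written, and nothing elsewhere in the documents repairs it. For growing nodules over 10 mm that meet the 400-day condition, it gives a value above 400 over at most about 12% of the qualifying growth range and over none of it in many 90-day cases, under the diameters and intervals assumed above. The rest read too low, negative or undefined. The reverse error, a faster-growing nodule reading above 400, is confined to growth just over 1 mm if negative values are not accepted as passing.

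The documents do not show that any participant was misclassified, and the number affected depends on how often volumetry was unavailable. The primary endpoint and sample size do not use VDT. The missing rule for zero or negative growth is a separate gap that correcting the formula will not close. The section 13.2 and Appendix C uses are secondary, and the conclusion does not rest on them.

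**What to change.** In section 7.6, replace the denominator with 3 × log10(maximum diameter at second CT / maximum diameter at first CT). Add one sentence on how zero or negative growth is read against the existing 400-day criterion, consistent with 4.1.5. The sponsor should confirm whether the Appendix C cut-offs ever relied on this formula. No threshold or clinical rule changes.

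Recalculate every diameter-based VDT used for eligibility or intended for the section 13.2 analysis. The text change is one line and one sentence, and recalculation is simple for enrolled participants without software volumetry. Among those enrolled, however, it can only detect wrongful entry. Wrongful rejection before consent is harder to trace, because section 6.8 ties the forms to consent: "Appropriate CRFs must be completed for any participant who signs an informed consent". Those candidates would have to be sought in screening files and in the EIO scans, which are "archived both on hard-disk and on CD in DICOM format". Complete recovery is not assured.
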